13.4.2.2 R0 Resection Rate

R0 resection rate and confidence intervals for the R0 resection rate will be calculated according to the approach of Duffy and Santner. Chi-square test (or Fisher's exact test if the data in contingency table is sparse) will be used to compare R0 resection rate between treatment arms. Sensitivity analysis will be conducted among patients in cohort 1) and cohort 2). The association between R0 resection rate and OS/PFS will be assessed by log-rank test and Cox model.

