In our initial pilot study we showed that FOLFIRINOX-based multimodality therapy for borderline resectable PDAC is well tolerated and study of this approach is feasible in the cooperative group setting [16]. 22 of 23 enrolled patients started therapy (median age 64 years, 64% ECOG PS 0). All patients completed mFOLFIRINOX and 21 (95%) completed CRT. Fourteen (64% [95% confidence interval (CI), 41-83%]) patients had grade ≥ 3 adverse events during preoperative therapy. The best RECIST radiographic responses during preoperative treatment were 2 CR, 4 PR, 14 SD and 2 PD. 7 patients did not undergo planned resection due either to progression (6) or refusal (1). 15 (68% [95% CI, 49–88%]) patients underwent pancreatectomy. Fourteen (93%) operations had microscopically negative margins, 5 (33%) operative specimens had $< 5\%$ residual viable tumor cells, and 2 (13%) specimens had pathologic complete responses. Overall survival of all patients at 18 months was 50%.

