11.4.3.1 Evaluation of Elevated CA19-9 Levels (When Present)

Note: this evaluation will be done for each patient for descriptive purposes only and will not be used to evaluate the secondary endpoint of progression free survival. Decision making for the efficacy of therapy and for relapse or progression must be based on imaging. Biochemical progression without the demonstration of objective progression of target or non-target lesion will not be sufficient indication to remove the patient from the study (refer to [Section 13.1](#)).

Biochemical Response (B-RESP): Reduction in elevated CA 19-9 level by at least 50% of normalization of an elevated value, confirmed with 2 successive measures.

Biochemical Progression (B-PROG): Increase in elevated CA 19-9 level by 50%, confirmed with 2 successive measures. If patient has had biochemical response as defined above, then subsequent biochemical progression is defined as >50% increase from the lowest recorded level while on study.

Biochemical Stability (B-STAB): Elevated CA 19-9 level does not change enough to qualify as response or progression.

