12.1.2 Disease Progression

Remove from protocol therapy any patient with disease progression as per [Section 12.1.3](#) or recurrence after surgery (either Arm 1 or Arm 2 patients). Document details, including tumor measurements, on data forms.

After disease progression, patients should be followed for survival per the study calendar ([Section 5.0](#)).

Note: Biochemical progression (B-PROG) without the demonstration of objective progression (PD) of target or non-target lesion will not be sufficient indication to remove the patient from the study (see [Section 11.4.3](#)).

12.1.3 Removal of Patients from Protocol Therapy:

In the absence of treatment delays due to adverse events, treatment will be completed unless the patient experiences any one of the following scenarios. The specific indication should be described as:

- Metastatic disease identified on imaging studies
- For patients with RECIST PD with local progression only, the treating investigator should decide whether continuing protocol treatment is in the best interest of the patient
- The presence of locally advanced disease on pre-surgical restaging imaging studies (see [Appendix II](#) for definition of locally advanced pancreatic cancer)
- Decline in PS in the absence of radiographic evidence for disease progression if PS cannot be recovered (symptomatic deterioration)
- Metastatic disease identified intraoperatively and biopsy-proven
- Unresectable disease identified intraoperatively (e.g., locally infiltrative disease without metastases for which the surgeon does not feel resection is safe)
- R2 surgical resection
- Nontherapeutic (aborted) operation for any other reason
- Intercurrent illness that prevents further administration of treatment
- Unacceptable adverse event(s)
- Patient decides to withdraw from the study
- General or specific changes in the patient's condition that render the patient unacceptable for further treatment in the judgment of the investigator

Patient should be removed from protocol therapy, and followed as per [Section 5.0](#), post-treatment follow-up. Protocol treatment will be discontinued and further treatment is at the discretion of the treating physician.

12.1.4 Follow-up for Patients Removed from Protocol Therapy:

For patients who are removed from protocol therapy in any instance listed in [Section 12.1.3](#), follow patients per the schedule found in [Section 5.0](#) of the protocol for clinical and survival status.

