13.1.2 Secondary Endpoints

13.1.2.1 R0 Resection Rate

R0 resection rate is defined as the proportion of patients in whom an achieved R0 resection was achieved during surgery (see [Section 11.7.2](#)). The R0 resection rate will be estimated in two cohorts, 1) patients who signed the consent form, deemed eligible by central review, and received any protocol defined treatment in each arm and 2) patients who signed the consent form, deemed eligible by central review, and underwent surgery in each arm. The R0 resection rate will be estimated by the number of patients in whom R0 resection was performed divided by total number of patients in cohort 1) and cohort 2) in each arm.

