13.1.2.2 Event-free Survival

Event-free survival is defined as time from randomization to the first documentation of event where events considered are 1) disease progression, per RECIST, prior to surgery, 2) surgery with R2 resection, 3) recurrent disease following surgery, or 4) death due to any cause.

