13.4.2 Secondary Endpoints

13.4.2.1 Event-free Survival

The distribution of event-free survival will be estimated using the method of Kaplan-Meier in each arm. Event-free survival will be compared between treatment groups using the log-rank test. The correlation between pCR status and event-free survival time will be assessed by Cox model with landmark approach.

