13.4.2.3 Pathologic Complete Response (pCR) Rate

pCR rate and confidence intervals for the pCR rate will be calculated according to the approach of Duffy and Santner. Chi-square test (or Fisher's exact test if the data in contingency table is sparse) will be used to compare pCR resection rate between two treatment arms. Sensitivity analysis will be conducted among patients in cohort 1) and cohort 2). The association between pCR rate and OS/PFS will be assessed by log-rank test and Cox model.

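### R0 and pCR are to be related to survival with no landmark, cohort or time origin; in all treated patients timed from randomization this favours R0 even when R0 has no effect

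*Combined protocol and SAP*

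**What the plan says.** Three sections of the analysis plan relate a surgical outcome to survival:

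- Section 13.4.2.1, pCR and EFS: "The correlation between pCR status and event-free survival time will be assessed by Cox model with landmark approach". The landmark time is not given.
- Section 13.4.2.2, R0: "The association between R0 resection rate and OS/PFS will be assessed by log-rank test and Cox model".
- Section 13.4.2.3, pCR: "The association between pCR rate and OS/PFS will be assessed by log-rank test and Cox model".

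The last two name no analysis set, start of time or landmark. Section 13.1.2.1 sets up two cohorts ("The R0 resection rate will be estimated in two cohorts"): all treated patients (cohort 1) and operated patients (cohort 2). Sections 13.4.2.2 and 13.4.2.3 mention both cohorts, but in a sensitivity-analysis sentence that follows the rate comparison, not in the association sentence.

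Sections 13.1.1 and 13.1.2.2 time the 18-month OS rate and EFS from randomization. EFS events include "1) disease progression, per RECIST, prior to surgery, 2) surgery with R2 resection". PFS is not defined in Section 13.1, although Section 11.4.3.1 treats it as a secondary endpoint, saying that CA 19-9 evaluation "will not be used to evaluate the secondary endpoint of progression free survival".

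**The concern.** R0 and pCR cannot be observed until the operation. If a patient's eventual R0 status is used as a baseline grouping from randomization, R0 patients have by construction survived to surgery, and every earlier death falls in the non-R0 group. The comparison then favours R0 whether or not R0 matters.

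For EFS there are two further problems. Progression before surgery is itself an event and usually prevents resection. R2 resection is non-R0 by definition and also an EFS event on the day of surgery, so restricting to operated patients does not remove the bias.

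The protocol gives R0 real weight: Section 1.1 calls complete resection a requisite of curative treatment, and Section 1.2 makes R0 the interim endpoint. An R0–survival hazard ratio from this trial could be read as support for R0 as an early marker when part or all of it reflects when R0 is recorded. Also, if PFS means EFS, Sections 13.4.2.1 and 13.4.2.3 prescribe different methods for the same pCR association.

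**Working it through.** **Plan figures.** The documents give no figure for these associations. The design figures that supply the inputs do reproduce. P(at most 11 of 30) is 0.431 at R0 40% and 0.0083 at R0 60% (stated 43% and 0.8%). P(at least 36 of 62) at 63% is 0.826, and 0.826 × (1 − 0.0083) = 0.819 (stated power 82%).

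**When R0 is known (Arm 1, no delays).** Cycle 8 starts at 7 × 2 = 14 weeks (Section 7.1.1). Surgery follows 4 to 8 weeks after the last chemotherapy, and treatment may start up to 14 days after registration (Section 7.0). The earliest time is 14 + 4 = 18 weeks and the latest 14 + 8 + 2 = 24 weeks, or 4.1 to 5.5 months.

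**Deaths before surgery under the plan's model.** Section 13.3 uses exponential survival with median 18 months (null) or 27 months (alternative). At the midpoint, 4.8 months, 1 − 2^(−4.8/18) = 17% and 1 − 2^(−4.8/27) = 12%.

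**Illustration by hand.** Take 100 treated patients, 18-month OS 50%, 50 of them R0, and no R0 effect after surgery. With a fraction e dead before surgery, 18-month survival is 0.50/(1 − e) in R0 patients. In non-R0 patients it is that value times (50 − 100e)/50.

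| Dead before surgery | R0 | Non-R0 |
|---|---|---|
| 17% | 60% | 40% |
| 10% | 56% | 44% |
| 5% | 53% | 47% |
| 2% | 51% | 49% |

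The whole gap comes from the grouping.

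**Simulation under no effect.** N = 62, surgery uniform at 18 to 24 weeks, overall R0 40 to 60% (both rates from Section 13.3), two-sided 5% test, censoring at 18 to 49 months, 2,000 trials per setting and a 60,000-patient run for each HR. For OS, R0 was assigned at random among patients alive at surgery. Survival was exponential, or piecewise with 2, 5 or 10% dead by month 5 and the same 18-month OS.

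| Analysis as written | Null HR | Rejection |
|---|---|---|
| R0–OS, all treated, exponential (12–17% early deaths) | 0.50–0.70 | 17–62% |
| R0–OS, all treated, 10% early deaths | 0.64–0.78 | 12–30% |
| R0–OS, all treated, 2–5% early deaths | 0.80–0.94 | 4–11% |
| R0–OS, operated only | 0.97–1.02 | near nominal |
| pCR–OS, pCR rate 9% (pilot 2/22) | 0.76–0.96 | 4–6% |
| R0–EFS, all treated, 27% events before surgery (pilot 6/22) | 0.29–0.67 | 31–98% |
| R0–EFS, all treated, 15% events before surgery | 0.54–0.80 | 12–53% |
| R0–EFS, operated only, R2 in 2–5% | 0.55–0.89 | 8–30% in favour of R0 (nominal 2.5%) |

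The all-treated EFS rows assume post-operative median EFS of 10 to 20 months. They let 0 to 25% of progressors still be operated, since Section 12.1.3 says: "For patients with RECIST PD with local progression only, the treating investigator should decide whether continuing protocol treatment" is in the patient's interest. The operated-only EFS row uses 37 operated patients with R0 in 80 to 85%, so about 6 to 7 are non-R0 (37 × 0.15 = 5.6; 37 × 0.20 = 7.4). R2 in 2 to 5% of 37 is about 1 to 2 patients. One or two events on the day of surgery in so small a group are enough to shift the HR.

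With both arms (N = 124), exponential survival with median 18 months and follow-up of 18 to 52 months, the null HR for R0–OS is 0.66, 0.60 and 0.51 at R0 40, 50 and 60%. Rejection is 48, 71 and 89%. The bias does not shrink with sample size; it is only detected more often.

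**With a 26-week landmark (N = 62).** R0–OS in all treated patients: HR 0.98–1.01, rejection 4–6%. R0–EFS in all treated patients: HR 0.97–1.02, rejection 4–7%. R0–EFS in operated patients: HR 0.97–1.03.

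**The case against.** The strongest reply is that the plan is silent rather than wrong. The OS bias needs cohort 1, randomization as origin and R0 as a fixed covariate, and the text commits to none of these in the association sentence. In cohort 2 the R0–OS bias disappears. That is true for OS. But the endpoint definitions start time at randomization, cohort 1 is the first cohort listed, and neither cohort is unbiased for R0–EFS.

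The second reply is about size. An overall R0 rate of 60% sits badly with the 40% expected not to reach surgery (Section 13.2): 60% of 62 is 37, so every operated patient would have to be R0. At 50% R0 the exponential runs give HR 0.58 to 0.66 and 25 to 44% rejection. The exponential model is used in Section 13.3 to convert medians to 18-month rates, not to predict early deaths. The pilot (Section 1.4.4) gives progression (6) and refusal (1), not death, as reasons for no resection. These points stand: with 2 to 5% early deaths the R0–OS test is inflated only slightly. They do not touch R0–EFS, which needs early progression rather than early death.

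Three other points also stand. The EFS figures hold only if PFS means EFS, and they rest on assumed R2 and post-operative rates. False positives for pCR–OS are not inflated. The landmark was tested only with all surgery complete before it, so patients operated later need a stated rule.

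**Conclusion.** The concern holds. Run as written in all treated patients from randomization, R0 against OS gives an HR below 1 with no true effect. The bias is large under the plan's own exponential survival and small if few patients die before surgery, and the documents do not report that share. R0 against EFS is the stronger case: it is biased in all treated patients because early progression is an event, and in operated patients because R2 is an event. For pCR the practical issue is the conflicting method, if PFS means EFS, and a moderate shift in the HR, not false positives.

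These are secondary association analyses. The interim rule (at most 11 of 30) and the final rule (at least 36 of 62) do not use them. A landmark removes the timing artefact; it does not remove confounding by prognosis, so an R0–survival association would still not be causal evidence.

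**What to change.** In Sections 13.4.2.2 and 13.4.2.3:

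- Extend the landmark of Section 13.4.2.1 to R0–OS, R0–EFS and pCR–OS.
- Set it at a stated time from randomization by which planned surgery is complete: 24 weeks plus a stated allowance for delays.
- Include patients alive (OS), or alive and event-free (EFS), at that time, and state how patients operated later are classified.
- State the cohort and the time origin for each association.
- Replace PFS with EFS, or define PFS in Section 13.1.2.

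A time-dependent R0 or pCR covariate is an adequate alternative for OS (null HR 0.99–1.01). It is not for EFS, because R2 is an event at surgery: the null HR is 0.76–0.89 if 5% of operations are R2.

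The cost is a few sentences of wording, with no new data or patients. Patients with events before the landmark leave these analyses: at 26 weeks about 5–21% for OS and 18–33% for EFS under the settings above. The R0–EFS question then becomes one about patients still event-free at the landmark, which excludes R2 resections before it, and the report should say so.

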13.4.2.3 Pathologic Complete Response (pCR) Rate

pCR rate and confidence intervals for the pCR rate will be calculated according to the approach of Duffy and Santner. Chi-square test (or Fisher's exact test if the data in contingency table is sparse) will be used to compare pCR resection rate between two treatment arms. Sensitivity analysis will be conducted among patients in cohort 1) and cohort 2). The association between pCR rate and OS/PFS will be assessed by log-rank test and Cox model.

13.4.2.4 Adverse Events (AE)

For CTCAE data, the frequency tables will be reviewed to determine the patterns. The overall adverse event rates will be compared between treatment groups using Chi-square test (or Fisher's exact test if the data in contingency table is sparse).

PRO-CTCAE data will, at minimum, be analyzed similarly to CTCAE data. Reasons for missed PRO-CTCAE assessments will be collected and we will describe the extent of missing data as well as its patterns and causes. The initial analysis of each PRO-CTCAE item will use all available scores in an analysis which mirrors the approach used for the CTCAE data. Supplemental analysis will use model-based multiple imputation incorporating baseline patient characteristics and physician-rated performance status (which is collected at each cycle). CTCAE data may be incorporated as axillary data into multiple imputation models for AEs which are captured by both PRO-CTCAE and CTCAE. Results from supplemental analysis will be descriptively compared to the results of the initial analysis to assess the robustness of results to missing data. Since a preferred or optimal statistical methodology for PRO-CTCAE data is yet to be determined, additional analyses of PRO-CTCAE data beyond those specified above may be undertaken based on the current state of the science at time of data maturity for this study.

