- †† Patients complete PRO-CTCAE by paper booklet ordered through the CTSU website. See [Section 9.1](#) for administration instructions. See [Appendix I](#) for PRO-CTCAE assessments for IRB submission and review only. See [Section 4.4](#) for ordering instructions. PRO-CTCAE booklets should be administered at the following time points: ≤ 21 days prior to treatment; day 1 of each cycle of mFOLFIRINOX (+/- 3 days); RT days 1-5 (Arm 2 only); prior to surgery (+/- 7 days); and day 1 of each cycle of FOLFOX (+/- 3 days).
- # For women of childbearing potential (see [Section 3.3.6](#)). Must be done ≤ 7 days prior to registration.
- A CA19-9 may be performed < 28 days prior to registration. Subsequently, CA19-9 may be performed +/- 14 days from the scheduled date. During treatment, CA19-9 should be performed every 28 days. For patients who have normal CA19-9 levels at baseline, continued testing of CA19-9 is not required.
- B EUS/fiducial marker placement must be attempted for patients in the RT arm. Immediately following review of first restaging studies, planning for EUS/fiducial placement and RT simulation should be scheduled to be performed during either cycle 5 or 6 of mFOLFIRINOX.
- C Restaging scans should be performed for both Arm 1 and Arm 2 at the following time points: 1) after the first 4 cycles of mFOLFIRINOX; 2) prior to surgery; 3) post-surgery but prior to first cycle of FOLFOX; 4) after 4 cycles while on FOLFOX. The baseline and restaging scan after completion of preoperative therapy and prior to surgery are to be centrally reviewed by the Alliance ICL at IROC Ohio per [Section 7.4.2](#). After protocol treatment, scans should be performed per the schedule indicated by footnote “****”.
- D Surgery-related AEs should be assessed and captured within 90 days of surgery.

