9.1 Routine Adverse Event Reporting

Adverse event data collection and reporting, which are required as part of every clinical trial are done to ensure the safety of patients enrolled in the studies as well as those who will enroll in future studies using similar agents. Adverse events are reported in a routine manner at scheduled times according to the study calendar in [Section 5.0](#). For this trial, the form, "Adverse Events: Solicited," is used for routine AE reporting in Rave.

PRO-CTCAE paper booklets ordered from the CTSU website are to be administered by a nurse/CRA and completed by the patient at scheduled times according to the study calendar in [Section 5.0](#), and then entered into Rave.

Solicited Adverse Events: The following adverse events are considered "expected" and their presence/absence should be solicited, and severity graded, at baseline and for each cycle of treatment by CTCAE, PRO-CTCAE, or both.

CTCAE v4.0 Term	PRO-CTCAE v1.0 Term	CTCAE v4.0 System Organ Class (SOC)
Blood bilirubin increased		Investigations
Hypoalbuminemia		Investigations
Wound infection		Infections and infestations
Bile duct stenosis		Hepatobiliary disorders
Diarrhea	Loose or watery stools (diarrhea)	Gastrointestinal disorders
Nausea	Nausea	Gastrointestinal disorders
Fatigue	Fatigue, tiredness, or lack of energy	General disorders
Weight loss		Investigations
Peripheral sensory neuropathy	Numbness or tingling in your hands or feet	Nervous system disorders
	Dry mouth	Gastrointestinal disorders
	Problems with tasting food or drink	Nervous system disorder
	Decreased appetite	Metabolism and nutrition disorders
	Vomiting	Gastrointestinal disorders
	Heartburn	Gastrointestinal disorders
	Bloating of the abdomen (belly)	Gastrointestinal disorders
	Pain in the abdomen (belly area)	Gastrointestinal disorders
	Itchy skin	Skin and subcutaneous tissue disorders
	Pain	General disorders
	Anxiety	Psychiatric disorders
	Sad or unhappy feelings	Psychiatric disorders

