13.1.2.4 Adverse Events (AE)

AEs and the maximum grade for each type of adverse events will be recorded for each patient separately for the following 3 periods:

1. During neoadjuvant chemotherapy and chemoradiation therapy
2. Surgical complications during surgery and post-op period for 90 days or prior to adjuvant therapy
3. During adjuvant therapy. See [Section 9.1](#).

Similarly, scores (0-4) and maximum score for each PRO-CTCAE item will be recorded for each patient separately for the 3 periods.

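### PRO-CTCAE is summarised by raw scores and raw per-period maxima, with no use of the pre-treatment score, so per-arm symptom rates include symptoms already present

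*Combined protocol and SAP*

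**What the plan says.** Objective 2.2.4 asks for the adverse event profile and safety of each arm by CTCAE and PRO-CTCAE together.

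- **Variables (13.1.2.4).** For CTCAE, "AEs and the maximum grade for each type of adverse events will be recorded for each patient separately" for three periods: neoadjuvant treatment, the surgical and postoperative period, and adjuvant therapy. Then: "Similarly, scores (0-4) and maximum score for each PRO-CTCAE item will be recorded for each patient separately for the 3 periods".
- **Analysis (13.4.2.4).** CTCAE is reviewed in frequency tables, and "The overall adverse event rates will be compared between treatment groups using Chi-square test", or by Fisher's exact test if the table is sparse. The initial PRO-CTCAE analysis "will use all available scores in an analysis which mirrors the approach used for the CTCAE data". A supplemental analysis uses multiple imputation with baseline patient characteristics and performance status. Further analyses are allowed, but none is specified.
- **Data collected.** The Section 5.0 footnote schedules booklets at "≤ 21 days prior to treatment; day 1 of each cycle of mFOLFIRINOX (+/- 3 days"), then during RT, before surgery and on day 1 of each FOLFOX cycle. Section 9.1 has the listed events "solicited, and severity graded, at baseline and for each cycle of treatment by CTCAE, PRO-CTCAE, or both". Its 15 PRO-CTCAE terms match the 15 numbered items in Appendix I, each with a 7-day recall.
- **Attribution.** Sections 8.2, 9.0, 9.3 and 9.4 bar the use of PRO-CTCAE for determining attribution.

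**The concern.** The items include abdominal pain, appetite, fatigue, anxiety and sadness, none of which is specific to the treatment. A patient who arrives with one of these and keeps it contributes a positive maximum in every period, exactly as a patient who develops it on study does.

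For CTCAE, the investigator's attribution gives some means of separating the two. PRO-CTCAE has none, so the patient's own pre-treatment score is the natural reference. The plan collects that score and then leaves it out of the summary. At stake is how the per-arm symptom profile is read. That profile is the main remaining use of these data now that Arm 2 is closed to enrolment and its treatment has ceased (Section 7.0).

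**Working it through.** The documents state no rate, sample size or power for PRO-CTCAE, so there is no planned figure to reproduce. The check is first of the text, then of the size under assumptions.

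**1. Text.** Sections 5.0 and 9.1 establish that a pre-treatment score exists for every listed item. Section 13.1.2.4 lists three periods, and baseline is not among them. Section 13.4.2.4 mirrors frequency tables and tests of rates. No section subtracts the baseline score, restricts counts to worsening or adjusts for the baseline score. In the PRO-CTCAE plan, baseline information enters only as patient characteristics in the supplemental imputation model.

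**2. Cycle 1 day 1.** A booklet is due then (+/- 3 days) with a 7-day recall, so its answers can mainly describe the week before dosing. The plan does not say whether this score counts towards the neoadjuvant maximum.

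**3. Overcount within an arm (assumed rates).** Let b be the proportion with the symptom at baseline (score 1 or more), all persisting into the period. Let t be the probability of new onset among the rest. Then:

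raw rate = b + (1 - b) × t

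The adjusted rate is the proportion scoring worse than baseline. It depends on how many patients with the symptom at baseline get worse. If they worsen with the same probability t, it equals t. If none worsens, it equals (1 - b) × t. With t = 30%:

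| b | Raw rate | Adjusted, same worsening | Adjusted, none worsens |
|---|---|---|---|
| 10% | 0.10 + 0.90 × 0.30 = 37% | 30% | 27% |
| 20% | 0.20 + 0.80 × 0.30 = 44% | 30% | 24% |
| 30% | 0.30 + 0.70 × 0.30 = 51% | 30% | 21% |

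With t = 0, the raw rate is simply b: a symptom rate with no new symptoms at all.

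**4. Between arms, no true difference.** Both arms were given the same b and t = 30%, with 62 per arm (Section 13.2), and a two-sided 5% chi-square test was simulated 200,000 times. The false-positive rate was 5.1%, 5.9%, 4.9% and 4.8% at b = 10%, 30%, 50% and 70%. Pre-existing symptoms do not manufacture an arm difference.

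**5. Between arms, true difference.** Assume t = 30% against 50%. The raw difference is (1 - b) × 20 points: 18 points at b = 10% and 14 at b = 30%. Power at 62 per arm, two-sided 5% (assumed), is Φ[(d - 1.96 × SE0)/SE1], where SE0 is the pooled and SE1 the unpooled standard error. For b = 30%, the rates are 51% and 65%:

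- SE0 = √(0.58 × 0.42 × 2/62) = 0.0886
- SE1 = √((0.51 × 0.49 + 0.65 × 0.35)/62) = 0.0877
- power = Φ[(0.14 - 0.1738)/0.0877] = 35%

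| b | Power, raw | Power, adjusted, same worsening | Power, adjusted, none worsens |
|---|---|---|---|
| 10% | 52% | 63% | 55% |
| 30% | 35% | 63% | 41% |

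The raw measure has the lower power in each case. How much lower depends on whether patients with baseline symptoms can also worsen.

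**The case against.** The strongest reply is that the plan does not forbid any of this. Section 13.4.2.4 sets a minimum, says that the best method for PRO-CTCAE was still unsettled, and allows further analyses when the data mature. Its wording about all available scores does not exclude the baseline booklet, and the word maximum comes from Section 13.1.2.4, not from the analysis section. That is fair: a baseline-adjusted summary is not excluded. It is also not planned, and a choice left to data maturity can be made after the scores have been seen.

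Three stronger readings are tempting, and the documents do not support them:

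- **That prior symptoms are counted as treatment effects.** PRO-CTCAE is barred from attribution, and objective 2.2.4 asks for a profile. What is inflated is the on-treatment symptom rate when it is read as new symptoms. As a measure of total symptom burden the raw rate is legitimate.
- **That the arm comparison is biased by baseline imbalance.** Patients are randomised, and chance imbalance is what the test allows for. The false-positive rates above confirm this. What remains is dilution and lost power.
- **That at 20% baseline prevalence only 24 of the 44 points reflect new worsening.** This treats every patient with a baseline symptom as unable to worsen. It is one end of a range of 24 to 30 points, and it rests on assumed rates.

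Two further objections stand in part. Baseline symptoms may not persist into the surgical and adjuvant periods, which would make the overcount smaller there. An adjusted score also gives 0 to a patient who is severe at baseline and throughout, so it cannot replace the raw maximum.

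**Conclusion.** The concern holds for the per-arm profile: on-treatment PRO-CTCAE rates will include symptoms already present, and the score that would separate them is collected but not used. Under the assumptions of 30% new onset and full persistence, baseline prevalence of 10-30% gives raw rates of 37-51%. The documents supply none of these rates, so the figures show the mechanism and not the expected result.

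In any between-arm comparison the consequence is dilution and lower power without systematic bias, and the closure of Arm 2 limits how much that comparison can show. This is a secondary-endpoint matter. The 18-month OS analysis does not use PRO-CTCAE. Nor do the stopping rules in Section 13.5, which rest on deaths and on attributed grade 4 or higher non-hematologic events. The change is still worth making because it is cheap and settles the choice in advance.

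**What to change.** In Section 13.4.2.4:

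1. For each PRO-CTCAE item and period, pre-specify a baseline-adjusted maximum: the maximum post-baseline score if it is worse than baseline, otherwise 0. Report it alongside the raw maximum.
2. Base statements about new or worsened symptoms, and any arm comparison, on the adjusted version. Use the raw maximum to describe total symptom burden.
3. State that a cycle 1 day 1 score completed before dosing is not counted as post-baseline.
4. Use patients with an observed baseline in the initial analysis, and handle missing baselines in the supplemental multiple imputation. That model needs a sentence to cover them, because the present text does not do so explicitly.

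The cost is SAP wording and one derived variable per item and period, with no new visits, booklets or patients. PRO-CTCAE would no longer mirror CTCAE exactly, which is reasonable given that only CTCAE carries attribution. Patients severe at baseline and throughout score 0 on the adjusted measure, which is why the raw maxima must be shown as well.
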